9. DESCRIPTIVE STATISTICS

9.1 Disposition of Patients

The number and percentage of patients meeting all inclusion criteria, completing (i.e. dying) and withdrawing will be summarised (Table 1), along with reasons for death and withdrawal from study.

9.2 Demographic and Baseline Characteristics

Patient demographics will be presented in Table 2.

Specific melanoma medical history is summarised in Table 3a which includes a summary of any lesions present during the screening period, by location. The number and percentage of patients with significant medical history (non-melanoma specific) since completion of study IMM-101-001 categorised by SOC and PT using MedDRA v 18.0 (or higher) will be presented in Table 3b.

Data summaries of pre-study administration by IMM-101 dose received since completing study IMM-101-001 can be found in Table 4. Pre-existing injection site reactions, and any history of severe local reactions following previous administration(s) of IMM-101 will be summarised as a frequency table (Table 5).

Previous medications are prescription/non-prescription drugs, vitamins, drugs of abuse and dietary supplements taken and stopped within 14 days prior to Day 0. Any previous medications stopped before 14 days prior to Day 0 will be identified with a flag in the listings. Any medications, including vitamins, and dietary supplements ongoing or started on/after Day 0 and surgical procedures are defined as Concomitant Therapies.

The incidence of patients receiving at least one anti-melanoma cancer therapy other than IMM-101 and ongoing or started on or after the first dose of IMM-101 in the FIH study will be summarised for the FIH and LTF studies combined. Overall incidence will be summarised as well as by therapy type and therapy verbatim term (i.e. description of treatment given). IMM-101 treatments and non-melanoma cancer therapies will not be included in the tabulation (Table 6). Concomitant treatments received during the FIH study were recorded in the FIH study CRF. Treatments for relevant medical history including relevant radiotherapy, cancer surgery, chemotherapy and immunotherapy received following completion of the FIH study and prior to entry to the LTF study and any medications taken within 14 days prior to the LTF study screening visit as well as concomitant treatments received after entry to the LTF study are recorded in the LTF study CRF.

9.3 Study Treatment, Exposure and Safety Outputs

An on-study administration table (Table 7) will show the number and percentage of patients who receive study drug and whether full dose or reduced dose was administered, summarised by visit. In these

presentations, the denominator for the calculation of percentages at each visit will be based on the number of patients available at each visit who provide a response.

A line graph for each patient will be plotted to visually display any variation in doses of IMM-101 (in mg) by time, during the LTF study. This will be presented in the form of a panel plot (Figure 1a) on standard axes for each patient. Each dose will be marked by an 'X' on the plot. In addition, a panel plot (Figure 1b) will be presented including all IMM-101 doses received from the first dose in the FIH study, to the last dose in the LTF study, inclusive including those taken whilst the patient was being treated in the NPP, in a similar manner.

Exposure, to include the time on LTF study in years, overall LTF study drug exposure (months) and total no. doses on study, will be summarised in Table 9a.

Overall exposure to IMM-101 from first dose in the FIH study to last dose in the LTF study inclusive will be summarised in Table 9b.

Summaries of adverse events will include the number of adverse events and the proportion of patients experiencing at least one adverse event. If an individual patient has more than one AE at a given level of classification the patient will be counted only once at the given level of classification but each event will be counted within the number of events associated with that level of classification.

All patients will have received IMM-101 in the context of both the Phase 1 study IMM-101-001, and, for the majority, during the NPP; therefore all AEs in this long-term follow-up study will be regarded as treatment-emergent.

Table 10a includes the incidence and frequency of all TEAEs, treatment emergent treatment-related AEs, treatment emergent SAEs, Serious treatment-related TEAEs, TEAEs resulting in withdrawal or death and AEs of NCI CTCAE Grade ≥ 3 .

Frequency summaries of treatment emergent adverse events by SOC and PT using MedDRA v 18.0 (or higher) will be included overall (Table 10b) and repeated to capture:-

- Treatment emergent adverse events of NCI Grade ≥ 3 (Table 10c)
- Treatment emergent, IMM-101-related, adverse events: AEs that are definitely, probably or possibly related to study drug or with an unknown relationship (Table 10d)
- Treatment emergent, SAEs (Table 10e)
- Treatment emergent adverse events leading to withdrawal or death (Table 10f).
- Treatment emergent non-serious adverse events (Table 10g).

Additionally, long term safety will be evaluated by combining treatment related adverse event experience in the FIH study through to the end of the LTF study by summarising treatment emergent treatment-related adverse events (IMM-101-001 and IMM-101-008 Combined) (Table 10h).

Where it is not applicable to grade an AE using NCI CTCAE grade, it will be excluded from the summary of NCI Grade 3 and above AEs. Any AEs with missing grades, however, will be included, based on a worst-case approach.

On-study injection site reactions are summarised over the treatment period by visit in Table 11.

Urine Pregnancy Test Results and blood samples for immunological markers will be listed but not summarised.

All safety data will be listed.

Any comments recorded as free text in the CRF will be listed.

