# **9. ASSESSMENT OF SAFETY AND TOLERABILITY**

## **9.1 SAFETY AND TOLERABILITY PARAMETERS**

The primary objective for this study is the evaluation of safety and tolerability based on:

- Local and systemic toxicities.
- Adverse Events with documentation of number, type and degree of toxicities as measured by the National Cancer Institute (NCI) Common Toxicity Criteria for Adverse Events (CTCAE) v4.0 where appropriate

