##### Adverse Events

Summary statistics will be presented descriptively for the following safety endpoints:

- Adverse Events - the number of AEs, the proportion of patients having at least one AE and AEs by coded terms will be presented.
- Related Adverse Events - the number of related AEs, the proportion of patients having at least one related AE and related AEs by coded terms will be presented. Related AEs are defined as events that are definitely, probably or possibly related to study drug or with an unknown relationship.
- Serious Adverse Events - the number of SAEs, the proportion of patients having at least one SAE and SAEs by coded terms will be presented.
- Adverse Events leading to withdrawal or death - the number of AEs, the proportion of patients having at least one AE and AEs by coded terms will be presented.

All AEs will be included in the patient listings and in the above summaries.

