8.3 Derived and Transformed Data

As age was not collected it will be derived using the patient's date of birth and date of consent. The derivation will be

Age (years) = integer part of ((patient informed consent date - date of birth + 1)/365.25).

Note that the full date of birth will be used in the calculation, but only year of birth will be listed. Patient initials will not be listed.

Time since initial diagnosis of current presentation, time since excision of primary lesion, time since excision of sentinel node and time since regional lymph node resection will be derived in years as follows;

Time since initial diagnosis of current presentation (years) = (Day 0 - date of initial diagnosis of current presentation + 1) / 365.25

Time since excision of primary lesion (years) = (Day 0 - date of excision of primary lesion + 1) / 365.25.

Time since excision of sentinel node (years) = (Day 0 - date of excision of sentinel node + 1) / 365.25 and missing if not excised.

Time since regional lymph node resection (years) = (Day 0 - date of regional lymph node resection + 1) / 365.25 and missing if not resected.

The relevant time variable above will be reported to 1 decimal place, but calculated using all accuracy available in the data. If any dates are partial, i.e. day number missing, the time variable will be calculated using month and year only and if day and month missing, the time variable will be calculated using year only as follows:

- If only month and year are present (MMYYYY): Time since Event = (Day 0 – Event date +1) / 365.25;
- If only year is present (YYYY): Time since Event = (Day 0 – Event date) +1 / 365.25.

The total number of pre-study doses of IMM-101 received (since the completion of study IMM-101-001) will be calculated for each patient.

Exposure during the IMM-101-008 study will be summarised by time on study in years and overall exposure in months, which will be derived using:

Time on study (years) = (date of study completion (i.e. death on study)/date of withdrawal) - Day 0 + 1) / 365.25.

Overall study drug exposure (months) = (date of last dose - date of first dose in study IMM-101-008 + 1) / 30.4375.

Overall exposure of IMM-101 (FIH and LTF study combined) will be derived using:
(date of last dose in study IMM-101-008 – date of first dose in study IMM-101-001 + 1) / 30.4375.

On-study dosing will be summarised using the total number of doses on study:

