Total no. doses on study = (Total number of IMM-101 doses whilst on the LTF study by totalling the doses (full or part doses counted as 1 dose) recorded in the CRF.

Time elapsed since previous dose (for on-study administration of IMM-101) will be derived using;

Time elapsed since previous dose (days) = (date of current dose - date of previous dose + 1).

A **dose change flag** (Dose changed from previous dose, I = increased, D = decreased) will be used to record any escalation or reduction in dose received between consecutive visits. If the dose has remained consistent compared to previous dose, this flag will remain unoccupied.

Time to event analysis will be performed on OS which will be calculated in years, from Day 0 in study IMM-101-008 using;

Overall Survival (years) = (date of death - Day 0 + 1)/365.25
OR (censored date - Day 0 + 1)/365.25

See Section 10 for additional information.

Adverse events and medical history will be coded using MedDRA v 18.0 (or higher). MedDRA will be used to create System Organ Class (SOC) and Preferred Term (PT) variables.

A **flag (Stopped >14 days prior)** will be created for previous medications which were taken and stopped before 14 days prior to the end of screening procedures (i.e. Day 0) based on the medication end date and date of Day 0.

Previous and concomitant medications and significant medical history since completing the FIH study will undergo coding for anti-melanoma cancer treatments, see Section 8.2.

Note: Derived variables recorded in the unit of months or years will be reported to 1 decimal place, derived variables recorded in the unit of days will be reported to whole numbers only. Age will be reported to whole years only.

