Note: Treatment emergent AEs are all those reported during the study. Related AEs are defined as events that are definitely, probably or possibly related to study drug or with an unknown relationship.

Note: CTCAE - Common Toxicity Criteria for Adverse Events CTCAE decode.

Note: Percent is based on total number of patients in the Safety Population.

Code: S:\Services\Immodulon\IMM-101-008\Analysis\Development\Code\Table10a.sas ddmmmyy:hh:mm:ss

Data: S:\Services\Immodulon\IMM-101-008\xxxxx.sas7bdat

Note to programmer: Please update data footnote with appropriate file directory.

CONFIDENTIAL**Exploristics Limited**

Identifier: EXP12002

Clinical Study Identifier: IMM-101-008

Final Analysis

Protocol: IMM-101-008

Analysis Population: Safety Population

Page x of y

Table 10b
Treatment Emergent Adverse Events

System Organ Class/ Preferred Term	N = xx n (%) m
Number of patients with treatment emergent adverse events (%)	xx (xx.x)
Total Number of treatment emergent adverse events	xx
System Organ Class	n (xx.x) m
Preferred Term	n (xx.x) m

Note: n = number of patients with an AE; m = number of AEs.

Hence if a patient has multiple AEs only one occurrence per person will contribute to 'n', but all occurrences will be counted under 'm' as this is the total number of events recorded.

Note: Preferred Term and System Organ Class are coded using MedDRA version x.xx.

Note: Percent is based on the total number of patients in the Safety Population.

Note: Treatment emergent AEs are all those reported during the study.

Code: S:\Services\Immodulon\IMM-101-008\Analysis\Development\Code\Table10b.sas ddmmmyy:hh:mm:ss

Data: S:\Services\Immodulon\IMM-101-008\xxxx.sas7bdat

Note to programmer: Please update data footnote with appropriate file directory.

Note to Programmer: Order by most common (by incidence) SOC and PT within SOC.

Note to programmer: Please add relevant version number in MedDRA note to reflect version used at time of coding.

CONFIDENTIAL**Exploristics Limited**

Identifier: EXP12002

Clinical Study Identifier: IMM-101-008

Final Analysis

Protocol: IMM-101-008

Page x of y

Analysis Population: Safety Population

Table 10c
Treatment Emergent Adverse Events with NCI CTCAE Grade \geq 3

System Organ Class/ Preferred Term	N = xx n (%) m
Number of patients with treatment emergent adverse events of NCI CTCAE \geq Grade 3	xx (xx.x)
Total Number of treatment emergent adverse events of NCI CTCAE \geq Grade 3	xx
System Organ Class	n (xx.x) m

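### The adverse event tables give counts and ever/never percentages without linking them to patient-time, so they cannot show AE burden per year or its change with continued dosing

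*SAP*

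**What the plan says.** Protocol 9.1 reads "The primary objective for this study is the evaluation of safety and tolerability based on" local and systemic toxicities and adverse events, and Protocol 4.1 lists the long-term safety profile as the first objective. Protocol 10.1.1.1 sets the AE measures: "the number of AEs, the proportion of patients having at least one AE and AEs by coded terms will be presented".

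SAP 9.3 carries this over: "Summaries of adverse events will include the number of adverse events and the proportion of patients experiencing at least one adverse event". In SAP 13.2, Table 10a lists numbers of patients and numbers of events. The shells of Tables 10b to 10f and 10h carry the notes "Note: n = number of patients with an AE; m = number of AEs" and "Note: Percent is based on the total number of patients in the Safety Population"; Table 10g has the same layout for non-serious events. No AE shell has a rate, a time period or a time to first event.

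Exposure is a separate output. SAP 9.3 assigns to Table 9a "Exposure, to include the time on LTF study in years, overall LTF study drug exposure (months) and total no. doses on study". SAP 8.3 defines the duration measure as "Overall study drug exposure (months) = (date of last dose - date of first dose in study IMM-101-008 + 1"), divided by 30.4375. The dose total is a count with "full or part doses counted as 1 dose".

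Other outputs do show time or dose. Table 7 gives full versus reduced dose by visit. Figures 1a and 1b plot mg per dose over time for each patient. Listing 10 lists mg, dose changes and days since the previous dose. Table 11 summarises injection site reactions by visit.

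**The concern.** SAP 1 says that the duration of the study is not fixed in advance, and patients leave at different times through death or withdrawal. When follow-up differs between patients, the percentage with at least one event depends on how long they stayed as well as on their risk. A total event count has the same weakness.

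The study exists because Phase I gave each patient only three doses (Protocol 4.2). A reader of a long-term safety report will want to know how many AEs occurred per year of treatment, and whether the later years look better or worse than the first. No planned AE table answers either question.

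A second, smaller matter concerns dose. Half doses are permitted (Protocol 7.5), but the Table 9a dose total does not distinguish them and no cumulative amount is planned.

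**Working it through.** **The documents' own figures.** Protocol 10.2 and 10.3 give no sample size or significance level, so there is no design calculation to reproduce. The Phase I ever/never percentages in Protocol 3.3 do reproduce: 18/19 = 94.7% (stated 95%) and 16/19 = 84.2% (stated 84%). The constants in SAP 8.3 agree: 30.4375 × 12 = 365.25. Since 95% of patients had an event in a study with a four-week dosing period, an overall ever/never row may have little room to vary over years.

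**Longest possible follow-up.** Protocol version 1.0 is dated 15 September 2011 (Protocol Appendix 4), and the Listing 1 footnote records termination in December 2018. From 15 September 2011 to 31 December 2018 is 2,665 days, and 2,665/365.25 = 7.3 years. This is an upper bound, because the documents give no enrolment dates and no actual follow-up times.

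**Ever/never percentage against follow-up.** With a constant event rate r and follow-up t years, P(at least one event) = 1 − exp(−r × t). The rates are assumptions; the documents give none for this study.

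| Assumed rate per patient-year | 1 year | 3 years | 7.3 years |
|---|---|---|---|
| 0.05 | 4.9% | 13.9% | 30.6% |
| 0.1 | 9.5% | 25.9% | 51.8% |
| 0.3 | 25.9% | 59.3% | 88.8% |
| 1.0 | 63.2% | 95.0% | 99.9% |

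Within each row the risk per year is the same throughout.

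**Event count against follow-up.** Rate per 100 patient-years = 100 × m/(N × mean years). With an assumed m = 30:
- N = 10: 300, 100 and 41 at mean follow-up of 1, 3 and 7.3 years.
- N = 12: 250, 83 and 34.

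The planned tables would show m = 30 in every case. The range for N is inferred. Protocol 4.2 has 18 eligible completers and 6 who had stopped by August 2011 (18 − 6 = 12), and the Figure 1a panel is laid out as 2 × 5 = 10.

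**Denominator.** Protocol 9.2 records AEs from consent and follows them to 30 days after end of study or withdrawal. Time on study in SAP 8.3 starts at Day 0. Screening lasts up to 28 days, so the mismatch is at most 28 + 30 = 58 days per patient. That is 58/365.25 = 16% of a one-year follow-up and 58/2,665 = 2% of the maximum.

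**Table 10h.** The Table 9b span runs from the first Phase I dose to the last dose in this study, so it includes the Named Patient Programme. Table 10h takes its AEs from the two studies; medical events in between were recorded as medical history. Phase I was completed by 23 September 2010, and from then to 15 September 2011 is 357 days. Taking that as a low-end gap, with 29 days of Phase I dosing, the gap's share of the span is:
- 1 year in this study: 357/(29 + 357 + 365.25) = 48%.
- 3 years: 357/(29 + 357 + 1,095.75) = 24%.
- 7.3 years: 357/(29 + 357 + 2,665) = 12%.

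Using that span unadjusted would dilute the rate.

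**Dose measures.** A dose every 28 days for 2,665 days is 96 doses. At 1 mg each the total is 96 mg; at 0.5 mg (0.05 mL of 10 mg/mL) it is 48 mg. The Table 9a count is 96 both times. The months measure ignores both amount and interval: a 36-month span could hold about 40 doses at 28 days, 13 at 91 days or 7 at 182 days (illustrative intervals).

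**The case against.** The strongest reply is that the package is better than the AE tables alone suggest. Table 9a gives N, mean, SD, median, minimum and maximum of time on study, so N × mean gives total patient-years and a reader could form one crude overall rate. Listing 1 gives each patient's time on study, and Listing 12 dates every AE. In about 10 to 12 patients these listings can be read directly. The AE measures are those the protocol specifies, and SAP 4 rules out inference, so no planned comparison is distorted. All of this stands. It makes the point one of presentation, but it does not supply a planned rate or any split by year.

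A reader might infer that the whole safety objective lacks a time dimension. The documents do not support that. Protocol 3.4 names injection site reactions as the main risk and an increase with repeated administration as a potential one. Table 11 reports them by visit, with a denominator of patients responding at that visit and an item on worsening with repeated doses.

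A reader might also infer that exposure as a whole treats a half dose as a full one. Only one of the three Table 9a measures does. The two durations do not depend on dose size, and reduced doses are visible in Table 7, Figures 1a and 1b and Listing 10. The counting rule is also not the cause of the missing AE rates.

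Two cautions about rates hold. Protocol 9.4 records each change in severity as a separate event, and Protocol 9.1.3.1 leaves it to the investigator whether an injection site reaction becomes an AE. Events per patient-year will therefore partly reflect recording practice. Rates by preferred term in so few patients would be driven by individuals.

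**Conclusion.** The point holds for the AE tables. Tables 10a to 10h report counts and ever/never percentages, are not linked to the patient-time in Table 9a, and so cannot show AE burden per unit of time or its change with continued dosing. It does not extend to local injection site reactions, and it is not true that the package contains no person-time.

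The size in this trial cannot be computed, because the documents give no event counts or follow-up times for it. The illustrations rest on assumed rates, an assumed 30 events, an inferred 10 to 12 patients and a 7.3-year upper bound. Under those assumptions the same event count corresponds to rates about sevenfold apart (300/41 = 7.3) between mean follow-up of 1 and 7.3 years.

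The dose-count gap is separate and less important: at most a two-fold difference in total mg that the Table 9a count cannot show. Taken together this is a cheap improvement to a descriptive plan, not the correction of an erroneous figure.

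**What to change.** - Keep n (%) and m as planned.
- Add total patient-years and events per patient-year to Table 10a and to the overall rows of Tables 10b to 10g. Do not add rates by system organ class or preferred term.
- Show the overall counts and rates of Tables 10a and 10d by year since Day 0, with the patient-years at risk in each year.
- Define the denominator in SAP 8.3. Either run it over the AE collection window (consent to 30 days after end of study or withdrawal), or keep time on study from Day 0 and restrict the numerator to events in that period. If the first is chosen, say where events between consent and Day 0 fall in the by-year split.
- Do not use the Table 9b span unadjusted as the denominator for Table 10h. Leave out the Named Patient Programme interval, or give no rate there.
- Add cumulative mg and number of reduced doses to Table 9a.
- Footnote that a change in severity counts as a new event.

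The inputs are already in Listings 1, 10 and 12, and SAP 11 provides for documenting such a change in the study report. The cost is some programming, slightly longer tables and rates that will be imprecise in about 10 to 12 patients.
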